7.5 Participants compensation

The survey participants may receive two types of compensation: primary (for the time spent and transportation costs associated with the participation in the survey) and secondary (for each recruited eligible respondent) (Annex 25. Compensation Log). The primary compensation is paid in monetary equivalent of \$11. During the formative assessment, the appropriateness of the amount will be examined, and, if needed, the amount may be revised in a particular city. In addition to monetary compensation, the survey participants will be offered informational materials on the prevention of HIV, HCV and syphilis, as well as condoms and syringes (provided by the available HIV prevention and harm reduction programs in the area).

The secondary compensation will be provided for recruiting each eligible participant who completed the survey. The status of coupons and eligibility of referrals will be recorded in the Compensation Log (Annex 25.). The amount of secondary compensation will be fixed as a monetary equivalent of \$7 for each successful referral.

In order to receive the secondary compensation, the participant will need to come to the site and fill in a short form about PWID who were invited for participation but refused a coupon (Annex 14. Form of refusal to participate in the survey for recruiters).

8.0 BIOLOGICAL COMPONENT

The biological component includes capillary blood collection with EDTA K3 blood micro containers for the purposes of rapid diagnostic tests for HIV, HCV, syphilis, the second HIV rapid diagnostic test, the third rapid HIV test, preparing DBS cards for detection of HIV recent infection and viral load (see Diagram 1).

This protocol involves the use of a diagnostic test labeled as research use only (RUO) in a way that is not in compliance with the manufacturer's certification or requirements. The Public health center will ensure that all applicable country laws/regulatory approvals related to investigational diagnostic tests, such as the one being used, have been obtained. CDC is not directly purchasing the tests, specifying the manufacturer, or in any way directing or requesting the off-label use of this assay during the implementation of this protocol.

8.1 Pre-test counseling

After completing the survey and before capillary blood collection, all participants undergo a pre-test counseling on HIV in accordance with the National Protocol on HIV testing services. Pre-test counseling includes clarification of the ways of contraction and transmission of HIV infection, HCV and syphilis, the significance of test results, the risks associated with injection drug use and risky sexual behavior, as well as prevention and treatment of HIV and sexually transmitted infections.

8.2 Capillary blood collection

[figure not shown]
In order to carry out all planned assays within the biocomponent, the collection of a total of 600 µl of blood (for HIV-negative and HIV-positive) is required. Additionally, 5 rapid tests and capillary blood collection from a finger means having up to four punctures, which may be too much for participants and result in their refusal to participate in the survey.

Capillary blood collection with EDTA K3 blood micro containers (microtainers) will ensure the sufficient quantity of blood necessary for all the subsequent stages of the survey, making testing algorithm less traumatic and prolonged for participants, and reducing the number of possible medical interventions and ensuring the required amount of capillary blood for all planned tests.

Samples of capillary blood will be obtained using EDTA K3 blood micro containers.

Capillary blood sample will be used to conduct the first HIV screening test, rapid tests for hepatitis C, syphilis, the second HIV rapid diagnostic test, third HIV test, and preparing the DBS cards for further laboratory detection of recent HIV infection and viral load.

Diagram 1. Graphic representation of HIV-testing algorithm

[figure not shown]

Diagram 2. Graphic representation of the testing algorithm for hepatitis C and syphilis

8.3 Rapid testing

For screening testing, rapid diagnostic tests (RDTs) will be used to detect serological markers of HIV, hepatitis C and syphilis, namely:

- HIV-1/2, Rapid Test for Antibody to HIV, Colloidal Gold Device, Beijing Wantai Biological Pharmacy Enterprise Co., Ltd., China;
- Hepatitis C Rapid Diagnostic Test (RDT) Rapid Anti-HCV Test, (Set №40), InTec PRODUCTS, INC, China;
- Syphilis Rapid Diagnostic Test (RDT) Anti-TP / First Response® Syphilis Anti-TP Card Test, Premier Medical Corporation Private Limited, India. Healthcare professionals will carry out testing according to the manufacturer's instructions and the SOPs of the survey.

When using rapid tests, it is possible to receive negative, positive or invalid results:

- in case of negative result of the first rapid test to detect HIV serological markers, the results are notified as negative to the participant according to the standard form No. 503-10/o of the results of rapid HIV test (Order of the MOH of Ukraine No. 794 of 2019) and information on

- the local NGOs providing preventive services to PWID is given;
- in case of a positive result of the first rapid test to detect HIV serological markers, the second rapid test is conducted;
- in case of invalid results on the first rapid test to detect HIV serological markers (absence of control mark), the testing procedure is repeated using the same test.

8.4 Second rapid HIV test

HIV-1/2.0, First Response v.3.0 Cards Kit, Premier Medical Corporation Private Limited, India, will be used to confirm the HIV-positive result of the first screening rapid test.

When using the second rapid diagnostic test, two results are possible: positive or negative results:

- in case of two positive test results to detect HIV serological markers, the third rapid test is conducted;
- in case of non-matching (discordant) results of two rapid tests (the first test is positive result, the second test is negative result), the repeated testing is carried out using the first rapid tests. If a negative result is obtained when test 1 is repeated, the participant is given a certificate of negative HIV test result (standard form No. 503-10/o of the results of rapid HIV test (Order of the MOH of Ukraine No. 794 of 2019); If a positive result is obtained when repeating Test 1, the test result is considered indeterminate and a certificate 503-10/o is given.

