7.0 PROCEDURES

7.1 Participant algorithm

Each participant will have to complete four stages of the survey; the approximate total duration to complete all steps is 82-195 minutes:

Completion of each stage has to be verified by the responsible staff in the Participants' Card (Annex 10. Participant's Card).

Stage:	STAGE 1. SCREENING			STAGE 2. BEHAVIORAL COMPONENT	
	Screening of potential participant	Coupon validation	Informed consent signing	Survey	
Responsible staff:	Coupon-manager Healthcare professional	Coupon-manager	Participant, involving coupon-manager	Interviewer	
Approximate duration:	5 minutes	1 minute	10-15 minutes	30-40 minutes	

Stage:	STAGE 3. BIOLOGICAL COMPONENT							
	Pre-test counseling	Capillary blood collection with EDTA k3 blood micro containers	Testing for HIV, hepatitis C, syphilis (rapid tests)	Second HIV rapid diagnostic test for those with first positive test	Third HIV rapid test for those, who are positive for first and second rapid tests	Blood collection for DBS to test the recent HIV-infection and viral load (for HIV-positives and those who stated that they are receiving ART)	Notifying participants of their testing results	Referral to HIV clinics (for HIV-positives) / Referral to HCF (for other)
Responsible staff:	Healthcare professional	Healthcare professional	Healthcare professional	Healthcare professional	Healthcare professional	Healthcare professional	Healthcare professional	Healthcare professional
Approximate duration:	5-10 minutes	5 minutes	10-15 minutes	10-20 minutes	10-20 minutes	3 minutes	10-20 minutes	5 minutes

Stage:	STAGE 4. COMPENSATION AND PEER RECRUITMENT				
	Primary compensation (participant)	Other PWID recruiting instruction	Other PWID recruitment	Other PWID participation in the survey	Secondary compensation (recruiter)
Responsible staff:	Coupon-manager	Coupon-manager	Participant	Participant	Coupon-manager
Approximate duration:	1 minute	5 minutes	up to 20 days	82-195 minutes	1 minute

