8.5 Third rapid HIV test

The third rapid test HIV-1/2, Bioline 3.0, Abbott Diagnostics Korea Inc, is used in the case of two positive test results with the tests HIV-1/2, Rapid Test for Antibody to HIV, Colloidal Gold Device, and HIV-1/2.0, First Response v.3.0 Cards Kit.

When using the third rapid HIV test, it is possible to receive positive and negative results:

- in case of the first test positive result and the second test positive result and the third test positive result to detect HIV serological markers, the result is recorded as "positive";
- in case of the first test positive result, second test positive result and third test negative result to detect HIV serological markers, the result is recorded as "indeterminate" and the participant is proposed to undergo re-testing in 14 days;

The test's result is given to the participant according to the standard form No. 503-10/o of the results of rapid HIV test (Order of the MOH of Ukraine No. 794 of 2019).

It's planned to provide the EQA HIV program 1 time and 3 times – for the internal QA program (1 time per month)

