8.6 Blood collection and DBS preparation

DBS samples are produced from EDTA capillary blood samples for each survey participant with positive results of the third HIV rapid test, and for 10% participants with HIV-negative result of the first rapid test, selected randomly in each city of survey, as well as for those participants who stated they are receiving ART in their questionnaires (Annex 23. DBS registration form).

One Whatman 903 Protein Saver Card (EU) DBS card should be filled with at least with 75 µl of blood

per circle. Sterile disposable pipettes with appropriate calibration are used to transfer a blood sample from a container with EDTA capillary blood to DBS card. It's necessary to turn the EDTA container 20 times before sample transfer. All other stages of DBS preparation must be carried out in accordance with the procedure specified in the relevant SOPs. The survey site healthcare worker will be trained in accordance with the CDC's instructions for this procedure; his/her competence will be checked by the national coordinator. The DBS cards are identified by a survey identification number and dried on a grid at room temperature at the testing sites. After drying, the cards are packed into hermetically sealed packages, along with the humidity indicator and the dryer, and forwarded to the Reference Laboratory for HIV/AIDS diagnostic (each new batch is forwarded in 10 days) by a transport service that guarantees the appropriate temperature conditions.

All test results are entered into the Test Results Form (Annex 15. Test Results Form).

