8.8 Post-test counseling and referral to services

HIV: All respondents undergo post-test counseling in accordance with the National Protocol of the HTS. The participants with HIV-positive result under the second and the third rapid diagnostic tests are informed by healthcare workers about the final result (Annex 17. Certificate of HIV test results) and referred on the same day to the nearest HIV clinic or ART site for ART initiation (Annex 16. Referral form for the survey participant; Annex 20. Registration log for referrals to HIV Clinics). During the data collection phase, representatives of local NGOs providing HIV testing and linkage services to PWID will be present at survey sites, and will enroll newly detected HIV positive participants in their projects, which provide active referral (accompanying) to HIV clinics and extended follow-up. The regional coordinator ensures the presence of social workers from a specialized NGO on the study site to accompany participants. If one social worker will not be enough, the regional coordinator will attract the necessary number of specialists to the site. Additionally, information on the referral to medical institutions, including the HIV clinic, is indicated in the informed consent that is provided to participant when he/she arrives at the site.

In accordance with the national procedure of ART prescription (Order of the Ministry of Health of Ukraine No. 551 of 2010), ART can be initiated immediately after an HIV-positive representative of a key groups is linked to care. The reluctance of HIV-positive participants to be registered with a HCF may be an obstacle to starting treatment the same day. Therefore, the specialized projects provide extended follow-up to ensure linkage to care when participant is ready for this.

If present in the city, additional referrals will be provided to social care and support projects (Annex 19. Social support referral form for the survey participant).

In case of HIV negative result all PWID who tested negative will be informed about PrEP options, which are available for free at the nearest HIV clinic/ART site. They will be offered to be accompanied by the social worker for PrEP initiation.

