To minimize the possibility of psychological discomfort, primary seeds will be recruited by the representatives of NGOs working with PWID, and participants will be recruited by their acquaintances. The interview will be conducted by a qualified interviewer. The interview will be conducted face-to-face in a private space in the presence of the interviewer and respondent only. The counseling and testing will be conducted by healthcare workers in specially designated private rooms in accordance with the national HIV counseling and testing recommendations. Participants with a positive test result will be informed that a final diagnosis is possible only after repeated testing at a HIV clinic. To minimize the stressful situations associated with obtaining positive test results, personnel trained in post-test counseling for people with first-time detected HIV will be involved. The survey personnel will also be able to refer participants who will need additional counseling services to non-governmental organizations, in particular, HIV treatment projects.

To protect confidentiality, any paper or electronic form will **not** contain names or other information that allows for participant's identification and will only be associated with the ID-code. Those who receive HIV-positive results will be asked to provide contact information for the organization of re-referral and treatment, which will only be accessible to the healthcare worker of the site.

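### Participants who report ART but test HIV-negative are routed to a negative result and a PrEP offer with no stated referral to clarify their status; the follow-up of an indeterminate result in 8.4 should also be checked against 8.5

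*Protocol*

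**What the plan says.** **ART reporters.** The stage table in section 7.1 lists dried-blood-spot (DBS) collection "for HIV-positives and those who stated that they are receiving ART". Section 8.6 repeats the rule: after third-test positives and a random 10% of first-test negatives, a DBS is taken "as well as for those participants who stated they are receiving ART in their questionnaires". The plan therefore foresees people who report ART without testing positive.

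For a negative first test, section 8.3 says "the results are notified as negative to the participant". Section 8.8 adds that "all PWID who tested negative will be informed about PrEP options", available at an HIV clinic or ART site, and offers a social worker to accompany them to start it. Neither section makes an exception for ART reporters. The referral step in 7.1 reads "Referral to HIV clinics (for HIV-positives) / Referral to HCF (for other".

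**Indeterminate results.** Section 8.4 covers a positive first test, a negative second test and a positive repeat of the first: "If a positive result is obtained when repeating Test 1, the test result is considered indeterminate and a certificate 503-10/o is given". Section 8.5 gives the same label to two positives followed by a negative third test and adds that "the participant is proposed to undergo re-testing in 14 days". For positives, section 14.4 states: "Participants with a positive test result will be informed that a final diagnosis is possible only after repeated testing at a HIV clinic".

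**The concern.** A person who says they take ART and then tests negative presents a conflict: either the report or the test is wrong. As written, that person can be told they are negative and offered PrEP before anyone is asked to resolve the conflict. If they are in fact infected and treated, the practical risk is that they stop treatment on the strength of the survey result. The plan uses the ART answer to decide on blood collection but not to decide on counselling or referral.

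The secondary concern is consistency. Two test patterns carry the same indeterminate label, but the written text asks only one of them back.

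**Working it through.** **1. The written end points, from 8.3 to 8.5** (T1, T2, T3 = first, second, third rapid test)

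| Sequence | Recorded result | Next step stated |
|---|---|---|
| T1− | negative | PrEP information and accompaniment (8.8) |
| T1+, T2−, repeat T1− | negative | as above |
| T1+, T2−, repeat T1+ | indeterminate | certificate only (8.4) |
| T1+, T2+, T3− | indeterminate | re-test proposed in 14 days (8.5) |
| T1+, T2+, T3+ | positive | same-day HIV-clinic referral (8.8); repeated testing (14.4) |

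Of five end points, three are non-negative. A further test is stated in the text for two of those three. This count takes 14.4 to mean a positive final result.

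**2. Following a test-negative ART reporter through the plan**

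- The questionnaire is completed before blood is taken (8.1), so the ART answer is known in time.
- The answer triggers a DBS (7.1, 8.6).
- The negative first test leads to a negative notification (8.3) and the PrEP information and offer (8.8).
- Same-day HIV-clinic referral in 8.8 is for positives, and 7.1 agrees.
- Section 8.7 says all DBS samples are tested for recency and viral load, though a later sentence there speaks only of HIV-positive samples. Viral-load results go to the HIV clinics to which participants are redirected. No such redirection is stated for this person. The instruction in 8.8 for collecting the result follows on from the positive-result case and relies on the ID number on the referral form.
- A high viral load would indicate infection. A suppressed one fits both effective treatment and no infection, so the DBS cannot settle the commonest question.

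**3. Size.** The documents give no count for either group. The range below is an assumption, with the same fraction in every city.

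- 5,000 × 0.001 = 5 people; 5,000 × 0.01 = 50 people, per group.
- If all of one group were misclassified, prevalence would move by at most 0.1 to 1.0 points.

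The precision formula, checked on the plan's own city-level figure in 4.4 (500 less 5% missing = 475, design effect 3.0, proportion 50%):

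- 1.96 × √(3 × 0.50 × 0.50 / 475) = 0.078, which matches the stated 50±8%.

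At 21% prevalence:

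- City: 1.96 × √(3 × 0.21 × 0.79 / 475) = 0.063, or ±6.3 points.
- Sentinel cluster (six cities, 3,000 less 5% = 2,850): 1.96 × √(3 × 0.21 × 0.79 / 2,850) = 0.026, or ±2.6 points.

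Viral suppression has a smaller denominator, so I checked its extreme: every test-negative ART reporter is infected and suppressed, added to the plan's 629 people living with HIV at 44% suppressed (0.44 × 629 = 276.8).

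- 0.1% of 3,000 = 3: (276.8 + 3) / 632 = 44.3%, a rise of 0.3 points.
- 1% of 3,000 = 30: (276.8 + 30) / 659 = 46.5%, a rise of 2.5 points.

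Both are inside the ±7 points that 4.4 plans for.

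**The case against.** The strongest reply concerns what is not shown. Diagram 1 is the natural place for the 8.4 branch to be drawn, and its figure is missing from the text at hand. Section 8.8 puts all post-test counselling under the National HTS Protocol, and 12.1 lists SOPs for testing, counselling and referral. Any of these may supply the re-test. Sections 14.4 and 14.9 also speak of a positive test result without requiring three positives, so someone with two reactive first tests could be read as covered. This largely stands: a reader might infer that 8.4 leaves such participants without follow-up, but the documents show only that its written text does not state one. Nor do they show that 14 days is the right interval for this different pattern.

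On ART reporters, a reader might infer that they have no route at all to clarify their status. That goes too far. Section 8.7 sends viral-load results to HIV clinics and has participants told they can obtain them, and 7.1 allows referral of others to a health facility. PrEP is only offered, and at a service that also provides ART, where the conflict may surface. What remains is that no HIV-clinic referral is stated for this group, the stated purpose of the accompanied visit is PrEP, and a suppressed viral load does not answer the question.

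It is also fair to object that ART use is unverified self-report. That is a good reason not to alter the serological result because of it, but not a reason to withhold a referral.

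**Conclusion.** The main point holds as a minor participant-safety improvement. Sections 8.3 and 8.8 apply the negative-result and PrEP pathway to everyone who tests negative on the first test, including a group that 7.1 and 8.6 expressly foresee, and the laboratory route in 8.7 does not close the gap. The secondary point is a check of 8.4 against sources not shown, not an established defect.

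A reader might also infer that prevalence or cascade estimates are biased, or that these participants should be reclassified as unresolved. The documents do not support either. The number affected is unknown, and under the assumed 0.1–1% any shift stays below the planned precision. Self-report alone is not a sound basis for overriding the rapid-test result. No survey estimate, precision or power figure changes materially.

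**What to change.** **Main change, in 8.3 and 8.8.** State that a participant who reports ART but tests negative is counselled not to stop ART on this result and is referred to the HIV clinic to clarify their status before any PrEP offer. Form 503-10/o can still report the rapid-test result. Record the disagreement between report and test as a note in the Test Results Form (Annex 15, which is not shown and may already have room for it). Keep the survey's rapid-test classification as it is; a sensitivity analysis can be added if wanted.

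**Secondary change, in 8.4.** Check Diagram 1, the SOPs and the National HTS Protocol for follow-up of the indeterminate result. If none has it, add a re-test proposal to 8.4 at the interval the national protocol sets.

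**Cost.** One or two sentences, one note and possibly one clause. No new information is needed on site, because the ART answer is collected before testing and already guides DBS collection. The downside is a few extra referrals, some prompted by inaccurate self-reports.

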8.5 Third rapid HIV test

The third rapid test HIV-1/2, Bioline 3.0, Abbott Diagnostics Korea Inc, is used in the case of two positive test results with the tests HIV-1/2, Rapid Test for Antibody to HIV, Colloidal Gold Device, and HIV-1/2.0, First Response v.3.0 Cards Kit.

When using the third rapid HIV test, it is possible to receive positive and negative results:

- in case of the first test positive result and the second test positive result and the third test positive result to detect HIV serological markers, the result is recorded as "positive";
- in case of the first test positive result, second test positive result and third test negative result to detect HIV serological markers, the result is recorded as "indeterminate" and the participant is proposed to undergo re-testing in 14 days;

The test's result is given to the participant according to the standard form No. 503-10/o of the results of rapid HIV test (Order of the MOH of Ukraine No. 794 of 2019).

It's planned to provide the EQA HIV program 1 time and 3 times – for the internal QA program (1 time per month)

